11.4.2. Analysis of Primary Efficacy Endpoint(s)

The primary efficacy variable will be total blood loss as described in Section 10.1. Since blood loss will be measured up to 24 hours after surgery and over the entire period of hospitalization, the primary measure will be the 24-hour level. Blood loss at later time-points will only be considered significant if the 24-hour measure has also reached statistical significance. Due to the hierarchical structure of this analysis, no adjustment for multiplicity will be performed.

The primary efficacy variables and continuous secondary efficacy variables will be analysed using Analysis of Covariance (ANCOVA) where one factor is treatment (TXA vs Placebo) and the other factor is Surgeon. The initial analysis will include the interaction between the

two factors in order to assess the similarity of effects across surgeons. Significant interaction effects will occur if (for example), TXA works for some surgeons but not for others. The final efficacy analysis will remove the interaction term and control for overall differences between surgeons.

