Exela Pharma Sciences has developed Tranexamic Acid Premixed Injection 10 mg/mL in 0.7% sodium chloride (1 gram tranexamic acid/100 mL). The pH of the product is 6.5 to 8.0 and the osmolality is approximately 285 mOsmol/kg. Exela is seeking FDA approval and registration for indications related to the reduction of perioperative blood loss.

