6.2. Rationale

As stated earlier, the CRASH-2 study established the safety and efficacy of tranexamic acid use in reducing blood loss in trauma situations and numerous reported studies support the safety and efficacy of tranexamic acid use for reduction of blood loss (or transfusions) in cardiac, gynecologic, and orthopedic surgeries. In addition, several surgical centers within the United States use tranexamic acid as part of their standard protocol during total knee-arthroplasty and hip replacement surgeries. However, this use of tranexamic acid is currently off-label. Exela intends to obtain approval for its tranexamic acid product for the indication of “reduction of perioperative blood loss”.

Several literature reported studies have shown tranexamic acid to be effective in reducing perioperative blood loss in spinal fusion surgeries.³⁻⁹ However, most of these studies showing efficacy of tranexamic acid in spinal surgery were conducted outside the United States and used varying dosing regimens. For example, one study reported by Shapiro F, et.al., conducted at Childrens Hospital Boston and Harvard Medical School used high doses of tranexamic acid (100 mg/kg administered over 15 min, followed by a 10 mg/kg infusion throughout the surgery).³ These authors reported that blood loss was reduced by 42% in the tranexamic acid treated group. A Canadian study by Wong J, et.al., reported a 25-30% reduction in blood loss using a 10 mg/kg initial dose

followed by a maintenance infusion of 1 mg/kg/h until skin closure.⁴ Another study by Grant JA, et al., compared a tranexamic acid bolus dose of 10 mg/kg followed by a 1 mg/kg/h infusion with a bolus dose of 20 mg/kg followed by a 10 mg/kg/h infusion in patients with idiopathic scoliosis and reported a 50% reduction in blood loss following the high dose.⁵ Verma K et al. reported a study plan to compare a low dose tranexamic acid regimen to a high dose tranexamic acid regimen for use in spinal fusion surgeries.⁶ A meta-analysis that consolidated the findings of 11 randomized controlled trials which investigated the use of TXA on surgical bleeding in spine surgery concluded that surgical bleeding and transfusion requirements are reduced using TXA and that there is no apparent association with increased incidence of pulmonary embolism, DVT, or MI.⁷

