8.2. Study Endpoints

8.2.1. Primary Endpoints

The primary endpoints of this trial are to assess:

1. Total Blood Loss based on changes in hemoglobin (Blood loss will be calculated by Nadler's and Gross's formulae from the time of admission to hospital until discharge; Hemoglobin and hematocrit concentrations will be measured pre-operatively, post-operatively, and at 24 h and every 24h thereafter until discharge).
2. Incidence of autologous or allogenic blood transfusion, including red blood cells and coagulation components (such as fresh frozen plasma and platelets).

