11.4. Statistical Analysis

11.4.1. General Approach

Data from multiple centers are intended to be combined under this protocol so that an adequate number of patients/subjects will be available for analysis.

Comparability of treatment groups based on demographic and baseline characteristics of the patients/subjects will be evaluated by appropriate statistical tests.

All hypothesis-testing analyses will be performed at the two-sided significance level of 5% ($\alpha=0.05$).

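### Two primary endpoints are declared, but the hierarchy used to justify no multiplicity adjustment covers only blood-loss time points; transfusion incidence is left out and no success rule is stated

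*Combined protocol and SAP*

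**What the plan says.** Section 8.2.1 lists two primary endpoints. The first is total blood loss calculated from haemoglobin and haematocrit. The second is "Incidence of autologous or allogenic blood transfusion, including red blood cells and coagulation components (such as fresh frozen plasma and platelets", a yes/no outcome per patient. The synopsis repeats both as endpoints and as objectives, Section 10.5 repeats both as primary objectives, and the purpose in Section 7 names both outcomes.

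Section 11 reads differently. Section 11.4.2 opens in the singular: "The primary efficacy variable will be total blood loss as described in Section 10.1". It makes the 24-hour value the primary measure and adds one gate: "Blood loss at later time-points will only be considered significant if the 24-hour measure has also reached statistical significance". From that gate it concludes: "Due to the hierarchical structure of this analysis, no adjustment for multiplicity will be performed".

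On models, the same section (and the synopsis) says "The primary efficacy variables and continuous secondary efficacy variables will be analysed using Analysis of Covariance (ANCOVA"), now in the plural. Section 11.4.3 assigns logistic regression, with Cochran-Mantel-Haenszel (CMH) as the fallback, only to categorical secondary variables, and transfusion incidence is not among those listed. On alpha, Section 11.4.1 says "All hypothesis-testing analyses will be performed at the two-sided significance level of 5" per cent. Section 11.1 gives one generic null hypothesis that names no endpoint. Section 11.2 sizes the trial on blood loss only.

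**The concern.** A fixed hierarchy is a valid reason for not splitting alpha, but only for the hypotheses placed in it. Here it holds blood loss at 24 hours and blood loss later. The second declared primary endpoint stands outside it and, under the blanket rule in Section 11.4.1, would be tested at its own full 5%. The justification therefore does not cover what the protocol calls primary.

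Without a success rule, three readings remain open, each with different error and power properties, and the choice could be made after the results are known. The trial is Phase III and is meant to support registration and labelling, so this decides whether a transfusion claim can be interpreted at all.

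Two related gaps bear on the same paragraph. Read literally, ANCOVA is the only model given for a yes/no primary endpoint. And the first step of any sequence needs a single time point: Section 11.4.2 says 24 hours, Section 8.2.1 runs to discharge without naming a primary time point, Section 10.5 defines the final haematocrit at 24 hours or at discharge/48 hours, and the abbreviation list defines it at 48 hours. Serial measurement to discharge is compatible with a 24-hour primary; the 48-hour text and the unnamed time point remain to be reconciled.

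**Working it through.** **Inputs from the documents.** Two-sided alpha 0.05 per test (11.4.1, 11.2); control mean 2000 mL, SD 1000 mL, 25% reduction, 80% power, 128 patients as 64 per group (11.2); 150 patients as 100 active and 50 placebo, with 14.7% loss allowed (11.2); no interim analysis (11.4.6). No transfusion rate is given anywhere.

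**The plan's own figure.** The difference is 0.25 × 2000 = 500 mL, so d = 500/1000 = 0.5. The two-sample t-test needs 63.8 per group, rounded up to 64, or 128 in total, with power 80.1%. The stated figure reproduces. The loss allowance also reproduces: 1 − 128/150 = 14.7%.

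**Reading A: either primary endpoint suffices.** With independent tests the familywise error is 1 − (1 − 0.05)² = 0.0975. For correlated test statistics (bivariate normal), it is 1 − P(|Z1| < 1.96 and |Z2| < 1.96):

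| Correlation (assumed) | Familywise error |
|---|---|
| 0 | 9.75% |
| 0.5 | 9.1% |
| 0.7 | 8.3% |
| 0.9 | 7.0% |

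**Reading B: both are required.** There is no inflation. Since P(both significant) ≤ P(blood loss significant), joint power is capped by blood-loss power. With noncentrality d·√(n₁n₂/(n₁+n₂)):

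- 100:50 gives 0.5 × √(5000/150) = 2.89 and power 81.8%.
- 85:43 (128 patients split about 2:1) gives 0.5 × √(3655/128) = 2.67 and power 75.5%.

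Below that cap the figures depend on assumed transfusion rates. The table uses a pooled z-test with exact binomial enumeration, unstratified, and multiplies by blood-loss power as if the tests were independent.

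| Control vs treated (assumed) | Transfusion power, 100:50 | Joint, 100:50 | Transfusion power, 85:43 | Joint, 85:43 |
|---|---|---|---|---|
| 40% vs 30% | 23.4% | 19.1% | 20.9% | 15.8% |
| 60% vs 45% | 43.3% | 35.4% | 35.0% | 26.5% |
| 80% vs 60% | 71.3% | 58.3% | 64.1% | 48.5% |
| 40% vs 24% | 52.8% | 43.2% | 46.8% | 35.3% |
| 60% vs 36% | 81.3% | 66.5% | 73.5% | 55.5% |
| 80% vs 48% | 97.8% | 80.0% | 95.5% | 72.2% |

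The first three rows are a 25% relative reduction and the last three a 40% reduction. Positive correlation raises joint power: at 0.5 and 100:50 the ranges become 22.4% to 63.5% and 48.6% to 81.0%.

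**Reading C: blood loss alone decides.** The error rate is 5% and the power is as sized. Transfusion is then not a primary endpoint, which contradicts Section 8.2.1 and the synopsis.

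**Comparison: even Bonferroni split.** At alpha 0.025, blood-loss power at 100:50 falls from 81.8% to 73.3%.

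**The case against.** The strongest reply is that blood loss is plainly the decisive endpoint. Section 11.4.2 names one variable and one primary measure, the trial is sized on it, and Section 6.1 says "Exela is seeking FDA approval and registration for indications related to the reduction of perioperative blood loss". No text says that either endpoint alone would suffice, so the inflated error rates describe the reading with the least support. The plural in the ANCOVA sentence could refer to the several blood-loss time points, in which case transfusion has no assigned model rather than the wrong one. Section 11.4.2 is the only place that designates a primary time point, so the 48-hour text may be a matter of definition. The joint-power grid rests on rates the documents do not give, and 75.5% assumes the full allowed loss, which Section 11.2 regards as unlikely.

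Much of this stands as a limit on size. The inflation is conditional, and under reading B only the cap is document-based. None of it removes the defect. If blood loss is the sole primary endpoint, Section 8.2.1, the synopsis and Section 10.5 are wrong to call transfusion primary. Whichever way the plural is read, a declared yes/no primary endpoint lacks a suitable analysis. Section 11 is complete in the document and contains no success rule.

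**Conclusion.** The concern holds and must be fixed before unblinding. The stated reason for no adjustment does not reach the second declared primary endpoint, and no rule links the two. What is established is a contradiction between the endpoint sections and the analysis section. An actual loss of error control follows only if either endpoint may support the claim; the rate is then 7.0% to 9.75% for correlations from 0.9 to 0. If both are required, error is controlled, but the stated 80% power describes blood loss only; joint power is at most 81.8%, or 75.5% if the full 14.7% is lost, and its actual value cannot be derived from the documents. If blood loss alone decides, error and power are as stated and the endpoint text is wrong.

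**What to change.** Rewrite Section 11.4.2 as a fixed sequence at two-sided 0.05:

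1. Total blood loss at the single primary time point, by ANCOVA.
2. Transfusion incidence, confirmatory only if step 1 is significant, by logistic regression with treatment and surgeon. CMH stratified by surgeon is the fallback, with its trigger fixed before unblinding (for example non-convergence, or a stated minimum number of transfused and non-transfused patients per model parameter).

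Later blood loss can be supportive and gated on step 1, or placed after step 2 in a stated order. That is the sponsor's choice, but it must not run beside step 2 as a second branch at full 0.05.

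If the agreed rule is that both endpoints must succeed, say so and restate the power as joint power. If blood loss alone decides, remove transfusion from the primary endpoints.

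Reconcile the primary time point across Sections 8.2.1, 10.5, 11.4.2 and the abbreviation list. Check the time point and the success rule against the FDA comments that the amendment history (version 1.3) gives as the reason for changing the endpoints. Correct the cross-reference in 11.4.2 from Section 10.1 to 10.5, where the formula stands.

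**Cost.** A protocol amendment before unblinding. The fixed sequence changes no sample size, visit or data item, and step 1 keeps its full alpha. The price is that transfusion cannot be claimed as confirmatory if step 1 fails, and later blood loss becomes supportive or testable only after transfusion succeeds. A both-must-succeed rule costs no alpha but puts the sample size in question.

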11.2. Sample Size Determination

Assuming a two-sided alpha level of 0.05, 80% power and estimated mean blood loss of 2000 mL in the control group (with a relatively low estimated standard deviation of 1000 mL due to limitations in the type of surgery and the patient population) a 25% decrease in blood loss in the treated group would require 128 patients (64 per group). Thus, the proposed sample size of 150 patients (100 active and 50 placebo) will allow 14.7% loss to follow-up which should be sufficient considering the relatively small likelihood of loss to follow-up in these patients.

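### The hierarchy in section 11.4.2 gates the later blood-loss time points on the 24-hour test but neither names nor orders them, so error for later claims is uncontrolled if there are two or more

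*Combined protocol and SAP*

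**What the plan says.** Section 11.4.2 makes total blood loss at 24 hours the primary measure. It goes on: "Blood loss at later time-points will only be considered significant if the 24-hour measure has also reached statistical significance". It then concludes: "Due to the hierarchical structure of this analysis, no adjustment for multiplicity will be performed".

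Section 11.4.1 sets the level for every test: "All hypothesis-testing analyses will be performed at the two-sided significance level of 5" per cent.

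Section 8.2.1 schedules hemoglobin and hematocrit, from which blood loss is calculated, "at 24 h and every 24h thereafter until discharge". Section 10.5 takes the final hematocrit in the formula at 24 hours, or at discharge or 48 hours after wound closure.

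No section lists the later time points to be tested, puts them in order, says what happens when one of them fails, or divides alpha among them.

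**The concern.** A hierarchy removes the need for adjustment when each test is allowed only after the one before it has succeeded. Section 11.4.2 describes one gate. Once the 24-hour test is significant, nothing in the text stops several later time points from each being tested at the full 5%. That arrangement protects the 24-hour claim but does not protect a set of two or more later claims. The trial is meant to support registration (section 7), so a claim of blood-loss reduction at a later time could be made under an error rate that the plan says is controlled and is not.

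A second, conditional point concerns who is compared. In-hospital values stop at discharge, and duration of stay is itself a secondary outcome (section 8.2.2). If later days were compared using only patients still in hospital, the groups would have been selected after randomisation.

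**Working it through.** **1. The plan's own figure.** Section 11.2 gives "Assuming a two-sided alpha level of 0.05, 80% power and estimated mean blood loss of 2000 mL in the control group". Its SD is 1000 mL, and the reduction sought is 25%, that is 0.25 × 2000 = 500 mL. The normal formula gives 2 × (1.960 + 0.842)² × (1000/500)² = 62.8, so 63 per group. The two-sample t-test version gives 63.77, so 64 per group and 128 in total. The stated figure is reproduced. Section 11.2 does not say which time point it refers to; I apply it to the 24-hour measure because that is the primary one.

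**2. How often the gate opens.** With 100 and 50 patients the expected 24-hour test statistic is 500 / (1000 × √(1/100 + 1/50)) = 2.887, and the chance of significance is 0.823. A larger true effect takes this towards 1.

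**3. No effect at any time.** A later claim requires a significant 24-hour test, so the chance of any false blood-loss claim is at most the chance of a false 24-hour result, 5%.

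**4. Real 24-hour effect, no later effect.** Let k be the number of later time points and ρ a common correlation between all the test statistics. Neither is in the documents. I assume k = 1 to 5 and ρ = 0.5 to 0.95. Write each statistic as √ρ·U + √(1−ρ)·E, with U shared and E separate, both standard normal. Given U = u, one later test is non-significant with probability

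A(u) = Φ((1.96 − √ρ·u)/√(1−ρ)) − Φ((−1.96 − √ρ·u)/√(1−ρ)).

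Let G(u) be the chance, given u, that the gate opens (mean 2.887 at the planned effect). The chance of at least one false later claim is the average over u of [1 − A(u)^k]·G(u), with G = 1 when the gate always opens. Numerical integration gives:

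| k | Gate always open: ρ = 0.95 | ρ = 0.9 | ρ = 0.5 | Planned effect, 100/50: ρ = 0.95 | ρ = 0.9 | ρ = 0.5 |
|---|---|---|---|---|---|---|
| 1 | 5.0% | 5.0% | 5.0% | 2.5% | 2.5% | 3.5% |
| 2 | 6.5% | 7.0% | 9.1% | 3.2% | 3.6% | 6.4% |
| 3 | 7.3% | 8.4% | 12.5% | 3.7% | 4.2% | 8.9% |
| 4 | 8.0% | 9.4% | 15.6% | 4.0% | 4.8% | 11.1% |
| 5 | 8.5% | 10.2% | 18.3% | 4.2% | 5.2% | 13.2% |

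A simulation with one million draws per setting agrees to within 0.1 percentage point. For reference, independent tests behind an open gate would give 1 − 0.95^k: 9.75% for k = 2 and 18.5% for k = 4.

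**5. With a fixed order.** The first later time point without an effect is tested at 5%, and nothing after it can be claimed unless it is significant. The chance of a false later claim is therefore at most 5% for every k and ρ. At the planned effect with no later effect it is 2.5% to 3.5%.

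**The case against.** The strongest reply is that only two measures are meant. Just before the rule, section 11.4.2 mentions loss up to 24 hours and loss over the whole hospital stay. If the sequence is 24 hours and then whole stay, it is a valid two-step fixed sequence, and the statement that no adjustment is needed is correct. Daily sampling is also not the same as daily testing, and no section says that every day will be tested. This stands as a possible reading, but it is not secured: the rule speaks of later time points in the plural, and section 10.5 offers both 48 hours and discharge.

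The size can also be challenged, and this largely stands. The higher percentages need several later tests, moderate correlation and a gate that is sure to open. Calculated blood loss at each time uses the same pre-operative hematocrit and the same estimated blood volume, so high correlation is plausible. At ρ = 0.9, the planned effect and k = 4, the figure is 4.8%, below 5%. A real effect at 24 hours with none at any later time is a worst case. It still counts, because an unqualified claim of error control has to cover it.

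Two stronger readings are tempting. A reader might infer that the primary result is inflated; it is not, because the 24-hour test comes first and is made once at 5%. A reader might also infer that later days will be analysed only in patients still in hospital. No section says so: section 11.3 makes all treated subjects the primary analysis population, and section 10.5 allows a discharge value. What is missing is a rule for patients already discharged.

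**Conclusion.** The concern holds in a limited form. The plan's reason for making no adjustment is sound for the 24-hour test and for one later measure. It fails once two or more later time points are tested, because they share one gate and have no order.

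In the worst case the chance of a false later claim exceeds 5% at every correlation tried for k = 2 or more. At the planned effect it ranges from below 5% to 13.2%, depending on k and ρ. These figures rest on assumed k and ρ, equal correlation and normal test statistics.

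Only later-time-point claims are affected, so the weight is between minor and something that should be corrected. The point about discharged patients is conditional on how the later comparisons are made. Transfusion incidence, the second primary endpoint in section 8.2.1, also has no place in this hierarchy; that is a separate issue, which the change below does not settle.

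**What to change.** In section 11.4.2, replace the open gate with a named, ordered list. For example: (1) blood loss at 24 hours; (2) at 48 hours, using the last in-hospital value for anyone discharged earlier; (3) at the last in-hospital value before discharge, for all mITT patients. Test each step at two-sided 0.05 only if the previous step is significant, and report all other days descriptively. If one whole-stay measure was intended, name it, define it for every mITT patient, and keep the two-step sequence without adjustment.

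The cost is one paragraph. The 24-hour test keeps the full 5%, and the sample size of 150 is untouched. The drawback is that a later time point cannot be claimed if an earlier one fails. If no order is acceptable, Holm's procedure across a named set of later time points, after the 24-hour gate, also controls the error, with stricter levels for those tests.

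Using the last in-hospital value keeps every treated patient in the comparison, but it is read at a time that differs between patients. The text should say so when the result is interpreted.

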11.4.3. Analysis of Secondary Efficacy Endpoint(s)

Secondary efficacy variables will include the following.

1. Blood loss measured as 3 times cell saver.

Also included as secondary efficacy variables will be several outcomes normally treated as adverse events.

1. Incidence of symptomatic anemia as defined in Section 10.1.

Categorical secondary efficacy variables will be similarly analysed using multiple logistic regression analyses. If incidences are low, analyses of interaction effects may not be possible and Cochran-Mantel-Haenszel tests will be used instead.

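### Transfusion incidence is a yes/no primary endpoint, but the plan gives it either ANCOVA or no stated analysis

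*Combined protocol and SAP*

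**What the plan says.** Section 8.2.1 and the synopsis list two primary endpoints. The first is total blood loss, which is continuous. The second is "Incidence of autologous or allogenic blood transfusion, including red blood cells and coagulation components", which is yes or no for each patient.

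The analysis text does not follow this split cleanly:

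- Section 11.4.2 and the Statistical Methods part of the synopsis both say: "The primary efficacy variables and continuous secondary efficacy variables will be analysed using Analysis of Covariance (ANCOVA". The factors are treatment and surgeon. The restriction to continuous variables is attached to the secondary variables and not to the primary ones.
- The treatment-by-surgeon interaction is fitted first, to compare the "two factors in order to assess the similarity of effects across surgeons", and is then dropped for the final analysis.
- Section 11.4.2 opens in the singular: "The primary efficacy variable will be total blood loss as described in Section 10.1". Its hierarchy concerns blood-loss time-points only, and transfusion is not named anywhere in it.
- Section 11.4.3 holds the plan's binary efficacy methods: "Categorical secondary efficacy variables will be similarly analysed using multiple logistic regression analyses". It adds a fallback: "If incidences are low, analyses of interaction effects may not be possible and Cochran-Mantel-Haenszel tests will be used instead".

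No section names a binary model, an effect measure or an interval for transfusion incidence.

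**The concern.** A secondary outcome, symptomatic anemia, has a binary model, while a primary yes/no outcome does not. Read literally, above all in the synopsis, where the ANCOVA sentence follows the list of both endpoints, transfusion goes into an equal-variance linear model.

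The variance of a proportion depends on its level. If TXA changes the transfusion rate, the two arms will in general have different variances. With equal arms, pooling would do little harm to the standard error of the difference. With 2:1 allocation the pooled variance is weighted toward the TXA arm, while the true standard error is driven mainly by the smaller placebo arm. Two outputs could suffer: any interval reported for the treatment effect, and the check of whether the effect is similar across surgeons. On the alternative reading, the model for a listed primary endpoint would be chosen without pre-specification, in a trial that section 7 says will support registration.

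**Working it through.** **The plan's own figure.** The only sample size in section 11.2 is for blood loss: a difference of 25% × 2000 = 500 mL, SD 1000 mL, 80% power, two-sided 0.05. A two-sample t-test calculation gives 63.77, so 64 per group and 128 in all, which matches. Section 11.2 gives no figure for transfusion; what carries over is the allocation of 100 TXA to 50 placebo.

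**Assumed inputs.** The documents give no transfusion rates, so a range is shown. They list eight sites but no number of surgeons; the simulations assume eight surgeons of near-equal size.

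**Interval.** ANCOVA on a 0/1 outcome estimates a risk difference. Write vT = pT(1 − pT) for TXA and vP = pP(1 − pP) for placebo.

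- Pooled SE = √{[(100 vT + 50 vP)/150] × (1/100 + 1/50)}
- True SE = √(vT/100 + vP/50)
- Coverage = 2Φ(1.96 × ratio) − 1, where ratio = pooled SE / true SE

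Example, TXA 10% and placebo 30%: vT = 0.09 and vP = 0.21. The pooled variance is (9 + 10.5)/150 = 0.13, so the pooled SE is √(0.13 × 0.03) = 0.0624. The true SE is √(0.0009 + 0.0042) = 0.0714. The ratio is 0.87.

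| TXA / placebo | SE ratio | Coverage of nominal 95% interval |
|---|---|---|
| 10% / 30% | 0.87 | 91.3% |
| 20% / 40% | 0.94 | 93.3% |
| 30% / 50% | 0.97 | 94.3% |
| 40% / 60% | 1.00 | 95.0% |
| 50% / 70% | 1.03 | 95.6% |
| 50% / 80% | 1.08 | 96.5% |
| 70% / 90% | 1.14 | 97.5% |

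The error reverses direction: too narrow when rates are low, too wide when they are high. Simulation with treatment and surgeon in the model (20,000 trials per setting) agrees: 94.0% at 30%/50%, 95.0% at 40%/60%, 96.0% at 50%/70% and 97.6% at 70%/90%. At the more extreme 5%/20% and 75%/95% it gives 89.4% and 98.4%. A variance estimate that allows unequal variances (HC3) held 94.7% to 95.9% in the simulated settings with a treatment effect.

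**Test of no effect.** With equal rates in both arms, from 5% to 95%, the ANCOVA treatment test rejected in 3.9% to 5.2% of trials, against 3.8% to 5.1% for Cochran-Mantel-Haenszel (CMH). With equal rates the variances are equal, so pooling does no harm.

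**Interaction check, surgeons identical.** The nominal 5% F test rejected in 21.5% of trials at 5%/20%, 10.5% at 15%/30%, 6.4% at 30%/50%, 4.7% at 40%/60%, 3.8% at 50%/70%, 2.5% at 60%/80% and 1.1% at 70%/90%. No surgeon differs here, so the distortion comes from unequal variances.

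**Interaction check, surgeons with different baselines.** Take a constant odds ratio of 0.4 and placebo rates of 20%, 50%, 70% and 90%. At 20% the odds are 0.25 × 0.4 = 0.1, a TXA rate of 9.1% and a difference of −11 points; the other three are −21, −22 and −12 points. With two surgeons at each rate, the F test rejects in only about 7% to 8% of trials. Other constant-odds-ratio settings with a treatment effect gave 6% to 15%.

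**The case against.** The strongest objection is that ANCOVA may never have been meant for transfusion. Section 11.4.2 begins with one primary variable and goes on to blood loss at 24 hours and later, so its plural could mean those time-points. That reading is fair, and a reader who infers that the plan unambiguously assigns ANCOVA to transfusion goes further than the text. But the reading leaves a listed primary endpoint with no analysis, and the synopsis lacks the singular sentence. Either way the same text needs correcting.

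A second objection is that the plan never promises a confidence interval: section 11.4.1 speaks of tests at the two-sided 5% level. This also stands. The coverage figures describe an interval taken from the ANCOVA, should one be reported, and not a stated deliverable. A reader might infer that the primary significance test is invalid; the rejection rates under equal arms do not support that.

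A third is that the surgeon check does not gate anything, since the interaction is removed whatever its result. That is correct, and it limits the harm to interpretation. A reader might also infer that the check is bound to show different effects because surgeons have different background rates. It is not: in the worked example it rejects only slightly more often than 5%. Nor are the differing risk differences spurious, since they are real on the scale that ANCOVA uses.

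**Conclusion.** The concern holds as a specification gap in the analysis of one of the two primary endpoints. Transfusion incidence is left with an equal-variance linear model or with no stated method, depending on which sentence of 11.4.2 governs.

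If ANCOVA is used, the test of no effect is sound. An interval from it would cover roughly 91% to 97.5% over assumed rates of 10%/30% to 70%/90% (TXA/placebo), with little error for rates of about 30% to 70% and none at 40%/60%. The treatment-by-surgeon test is less dependable: with identical surgeons it can reject from about 1% to over 20% of the time, mainly because of unequal variances. Differing baselines under a constant odds ratio add a modest excess. These sizes rest on the assumed rates and, for the interaction, on eight near-equal surgeons. The gap in the text rests on neither. This point concerns the model only, not multiplicity between the two primary endpoints.

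**What to change.** In 11.4.2 and in the synopsis, limit ANCOVA to the continuous primary variable, total blood loss. Then state that transfusion incidence will be analysed as the plan already does for categorical variables: logistic regression with treatment and surgeon, and CMH stratified by surgeon if incidences are low or strata are sparse.

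Name one effect measure with a matching 95% confidence interval, and assess surgeon heterogeneity on that same scale. An odds ratio goes with a heterogeneity test on the odds-ratio scale; a risk difference goes with one on the risk-difference scale. Mixing the two would make the check answer a different question from the estimate. Amend the singular opening of 11.4.2 so that it agrees with the two endpoints in 8.2.1.

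The cost is a few sentences in two places, with methods already in the plan. It needs no new data and no more patients.
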